3.2 Rationale of study design

The randomized, double-blind, placebo-controlled design used in this study is aligned with the Phase III trials of secukinumab, and with previous studies performed in the indication of chronic plaque psoriasis, and is in accordance with health authority guidelines and feedback, including the United States Food and Drug Administration (FDA).

The study population consists of adult subjects with moderate to severe plaque-type psoriasis who are candidates for systemic therapy or phototherapy.

The primary analysis time point of the trial is at Week 12. This is in line with the timing of the primary analysis time point in the secukinumab Phase III trials, and will allow for assessment of

efficacy at a point in time for which efficacy data from currently approved biologic therapies are available. However, as the study design provides for treatment duration of up to 52 weeks, it also allows for the assessment of longer-term safety and tolerability of secukinumab in this population. For subjects randomized to receive placebo at Visit 2/Baseline, the 52-week treatment duration allows these subjects the opportunity to receive up to 40 weeks of treatment with secukinumab.

Patients with moderate to severe psoriasis have a clinically significant increased risk of major cardiovascular events and mortality independent of traditional risk factors. Treatments that improve not only the skin manifestations of psoriasis but also its cardiovascular co-morbidities are of intense clinical and scientific interest. Measurement of aortic inflammation by FDG-PET/CT is a reproducible, operator independent, prognostic marker of future vascular events (Figueroa et al 2013; Mehta et al 2012). Furthermore, it responds to statins and modulates in a short time frame (i.e., within 12 weeks) unlike alternative approaches such as carotid intima-media thickness (IMT) and MRI-based measures of wall thickness (Tawakol et al 2013).

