4.2 Exclusion criteria

Subjects fulfilling any of the following criteria are not eligible for inclusion in this study. No additional exclusions may be applied by the Investigator, in order to ensure that the study population will be representative of all eligible subjects.

1. Forms of diagnosed psoriasis other than chronic plaque psoriasis (e.g., erythrodermic, generalized or localized pustular psoriasis, or new onset guttate psoriasis)
2. Medication-induced or medication exacerbated psoriasis (e.g., new onset or current exacerbation from beta-blockers, calcium channel inhibitors or lithium)
3. Previous exposure to secukinumab or any other biologic drug directly targeting IL-17A or IL-17RA receptors (e.g., ixekizumab, or brodalumab)
4. Diagnosis of other active ongoing skin diseases or skin infections (bacterial, fungal, or viral), or inflammatory diseases other than psoriasis that may interfere with the evaluation of psoriasis
5. Subjects not willing to limit UV light exposure (e.g., sunbathing and/or use of tanning devices) during the course of the study

6. Ongoing use of prohibited psoriasis treatments (e.g., topical or systemic corticosteroids, other topical medications, systemic psoriasis treatments oral or biological, UV therapy); washout periods detailed in the protocol must be followed (Table 5-2)
7. Use of any investigational drug within 4 weeks prior to Randomization, or within a period of 5 half-lives of the investigational treatment prior to Randomization, whichever is longer
8. Subjects using cholesterol-lowering medication (e.g., statins) and not on a stable dose for at least 90 days prior to randomization and unable to remain on a stable dose for the duration of the study
9. Pregnant or nursing (lactating) women, where pregnancy is defined as the state of a female after conception and until the termination of gestation, confirmed by a positive human chorionic gonadotropin (hCG) laboratory test
10. Women of child-bearing potential, defined as all women physiologically capable of becoming pregnant, unless they are using effective methods of contraception during dosing of study treatment and for 16 weeks after stopping treatment. Effective contraception methods include:
 - Total abstinence (when this is in line with the preferred and usual lifestyle of the subject. Periodic abstinence (e.g., calendar, ovulation, symptothermal, post-ovulation methods) and withdrawal are not acceptable methods of contraception

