5.3 Treatment Assignment, randomization

At Visit 2/Baseline, all eligible subjects will be randomized via Interactive Response Technology (IRT) to one of two treatment groups. The Investigator or his/her delegate will contact the IRT after confirming that the subject fulfills all the inclusion/exclusion criteria. The IRT will assign a randomization number to the subject, which will be used to link the subject to a treatment group and will specify a unique medication number for the first box of study treatment to be dispensed to the subject. The randomization number will not be communicated to the caller.

The randomization numbers will be generated using the following procedure to ensure that treatment assignment is unbiased and concealed from subjects and Investigators/site staff. A subject randomization list will be produced by the IRT provider using a validated system that automates the random assignment of subject numbers to randomization numbers. These randomization numbers are linked to the two different treatment groups, which in turn are linked to medication numbers. A separate medication list will be produced by or under the responsibility of Novartis Drug Supply Management (DSM) using a validated system that automates the random assignment of medication numbers to boxes containing the study treatments(s).

The randomization scheme for subjects will be reviewed and approved by a member of the Novartis Biostatistics Group.

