5.5.7 Concomitant treatment

All treatments administered during the six months prior to the Randomization visit (including any treatments started during the screening period) for any reason NOT including psoriasis will be entered on the Prior and Concomitant Medications eCRF or the Surgical and Medical Procedures eCRF with the reason for administration.

Psoriasis treatments used from the time the subject started to treat his/her psoriasis will be reported on the Prior Psoriasis Therapy eCRF. All topical treatments, systemic treatments, and phototherapies for psoriasis administered prior to randomization will be recorded ([Section 6.2.2](#)).

The Investigator should instruct the subject to notify site staff about any new treatments he/she takes after the start of the study treatment. All medications and significant non-drug therapies (including physical therapy and blood transfusions) administered after the subject starts study treatment must be recorded on the Prior and Concomitant Medications eCRF or the Surgical and Medical Procedures eCRF as appropriate. Information recorded will include indication for use, dosage, and dates of administration.

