5.5.8 Prohibited Treatment

Use of any treatments displayed in [Table 5-2](#) that could confound the efficacy of the study drug are **not** allowed during the study for any indication; wash-out periods for these treatments are provided in [Table 5-2](#). If the use of these treatments is required, then the subject must **not** be randomized into the study.

The Investigator/qualified site staff must instruct the subject to notify them about any new treatments he/she takes after the start of the study treatment. All prohibited medications and significant non-drug therapies administered after the subject starts study treatment must be listed on the Prior and Concomitant Medications eCRF and the Surgical and Medical Procedures eCRF as appropriate, or the Concomitant Medications-Topical Corticosteroids eCRF for any TCS used after randomization.

If a prohibited treatment listed in [Table 5-2](#) was used during the study, the subject must discontinue use of the prohibited treatment if he/she wishes to continue in the study. If, in the Investigator's clinical judgment, the subject's use of a prohibited treatment presents an undue safety risk for the subject, the subject **must** be discontinued from study treatment as per [Section 5.5.9](#).

If a subject receives a live virus vaccination during the study, the subject **must** discontinue study treatment and complete an end-of-treatment visit (either Visit 8/Week 12 EOT1 or Visit 14/Week 52 EOT2).

Any other protocol deviation that results in a significant risk to the subject's safety will be recorded.

Exposure to light

Subjects will be advised to limit exposure to ultraviolet (UV) light (including sunbathing and/or use of UV tanning devices) during the study to avoid possible effects on psoriasis.

Table 5-2 Prohibited treatment

Prior Therapy (Before Visit 2/Baseline)	
Prohibited Treatments^{†,‡}	Washout Period (before Randomization)
Secukinumab	No prior use allowed
Any biologic drug directly targeting IL-17 or the IL-17 receptor (other than secukinumab)	No prior use allowed
Alefacept, briakinumab, efalizumab, ustekinumab	6 months
Biological immunomodulating agents other than above (e.g., adalimumab, infliximab, etanercept)	3 months
Cholesterol-lowering medication (e.g., statins)	Dose must be stable for ≥90 days prior to randomization and remain stable for the duration of the study

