### 5.5 Rule of exclusion criteria of analysis sets

**Table 5.1 Protocol deviations that cause subjects to be excluded from analysis**

Deviation ID	Description of Deviation	Exclusion in Analyses	Severity code
INCL0 1	Patients have not signed Informed Consent Form prior to initiation of any study-related procedure.	Excluded from FAS and SAF	3
	Age criteria not met	Excluded from none of the analysis set	0
INCL0	Date of diagnosis of plaque psoriasis is greater than or equal to 6 months prior to randomization	Excluded from none of the analysis set	0
INCL0	No Moderate to severe plaque psoriasis at Baseline Visit	Excluded from none of the analysis set	0
INCL0	Subject with systemic therapy are not inadequately controlled by topical treatment and/or phototherapy and/or previous systemic therapy for Plaque psoriasis.	Excluded from none of the analysis set	0

Deviation ID	Description of Deviation	Exclusion in Analyses	Severity code
INCL06	Physical examination, FDG-PET/CT scan without clinically significant findings, clinical laboratory results within laboratory ref ranges or abnormal results are deemed to be not clinically significant.	Excluded from none of the analysis set	0
EXCL01	Forms of psoriasis other than chronic plaque-type psoriasis	Excluded from none of the analysis set	0
EXCL02	Medication induced psoriasis or medication exacerbation psoriasis	Excluded from none of the analysis set	0
EXCL03	Previous exposure to secukinumab or any other biologic drug targeting IL-17A or the IL-17RA	Excluded from none of the analysis set	0
EXCL04	Diagnosis of other ongoing active skin diseases or skin infections or inflammatory diseases other than psoriasis.	Excluded from none of the analysis set	0
EXCL05	Unwillingness to limit UV light exposure (sunbathing and/or use of tanning devices)	Excluded from none of the analysis set	0
EXCL06	Prohibited medications used/washout period not observed/Other treatments known to worsen psoriasis not stable for 4 weeks before randomization	Excluded from none of the analysis set	0
EXCL07	Use of Other investigational drugs within 5 half-lives or 4 weeks prior to randomization, whichever is longer	Excluded from none of the analysis set	0
EXCL08	Use of unstable dose of cholesterol-lowering medications for at least 90 days prior to randomization	Excluded from none of the analysis set	0

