EXCL21	Presence of a medical or psychiatric condition that renders subject unable to adhere to protocol/complete the study	Excluded from none of the analysis set	0
EXCL22	History or evidence of drug or alcohol abuse within the 12 months prior to screening.	Excluded from none of the analysis set	0
EXCL22A	History or evidence of not willing to limit alcohol use to less than or equal to 14 drinks per week within 4 weeks prior to screening or anytime during the study.	Excluded from none of the analysis set	0
EXCL23	History of hypersensitivity to constituents of study treatment and/or allergic to rubber or latex	Excluded from none of the analysis set	0
EXCL24	Subjects who are not able and/or not willing to self-administer secukinumab injections or who have no trained caregiver available to administer the injections	Excluded from none of the analysis set	0
TRT01	Incorrect, missed or partial doses of study medication administered by subject	Excluded from none of the analysis set	0
TRT02	Incorrect study drug administered at any time during the study	Excluded from none of the analysis set	0
COMD01	Use of prohibited treatment at any time during the study after randomization	Excluded from none of the analysis set	0
COMD02	Receipt of a live virus vaccination during the study	Excluded from none of the analysis set	0
OTH01	Missing psoriasis efficacy assessment at any endpoints (IGA, PASI)	Excluded from none of the analysis set	0
OTH02	ICH-GCP non-compliance of study site in the study	Excluded from none of the analysis set	0
OTH03	Informed consent process or documentation deficiencies	Excluded from none of the analysis set	0

Deviation ID	Description of Deviation	Exclusion in Analyses	Severity code
OTH04	First drug administration and/or Date of Visit 2 is not within 7 days of Baseline (Visit 2) FDG-PET/CT scan	Excluded from none of the analysis set	0
OTH05	Failure to perform key study procedures (example FDG-PET/CT scan, cardiometabolic biomarker blood draw)	Excluded from none of the analysis set	0
WITH1	ICF withdrawn but patient continuing in the study	Excluded from none of the analysis set	0

Protocol deviations will lead to subject classification into the analysis sets as follows:

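### Exclusion 8 joins its two statin-stability failures with *and*, so it excludes fewer subjects than Table 5-2 requires; it should read *or*

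*Protocol*

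**What the plan says.** Protocol Section 4.2, Exclusion 8, applies to subjects on cholesterol-lowering medication who are "not on a stable dose for at least 90 days prior to randomization and unable to remain on a stable dose" for the rest of the study. The row for the same drugs in Table 5-2 (Section 5.5.8) reads "Dose must be stable for ≥90 days prior to randomization and remain stable for the duration of the study".

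Three other places bear on how a site would apply these texts:

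- Section 5.3 has the investigator contact the randomization system "after confirming that the subject fulfills all the inclusion/exclusion criteria".
- Section 4.2 opens by stating that any one criterion excludes and that investigators may not add exclusions of their own. Within that list only Exclusion 6 refers to Table 5-2 ("washout periods detailed in the protocol must be followed (Table 5-2"), and Exclusion 6 concerns psoriasis treatments.
- SAP Table 5.1 defines deviation EXCL08 as "Use of unstable dose of cholesterol-lowering medications for at least 90 days prior to randomization", with code 0, so the subject stays in every analysis set.

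On why stability matters, Protocol Section 3.2 says of the imaging measure that "it responds to statins and modulates in a short time frame (i.e., within 12 weeks". Section 6.4.6 puts the improvement with statins at within four weeks.

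**The concern.** The eligibility list and Table 5-2 state different rules for the same subjects. A subject who started or changed a statin a month before randomization, and who intends to stay on the new dose, passes Exclusion 8 and fails Table 5-2. A site working from the eligibility list would randomize that subject. A site that refuses the subject on the strength of Table 5-2 could be told that it has added an exclusion.

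At stake is the primary endpoint, the Week 12 change in TBR. Part of a recent statin effect could fall between the baseline and Week 12 scans. The primary ANCOVA has terms for treatment, baseline and body-weight stratum only, so nothing in it would absorb that change.

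**Working it through.** **Logic.** Let A = dose stable for 90 days before randomization, and B = able to keep the dose stable during the study.

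- Exclusion 8 as written excludes when (not A) and (not B).
- A breach of Table 5-2 is not (A and B), which equals (not A) or (not B).

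| A | B | Exclusion 8 as written | Breaches Table 5-2 | Exclusion 8 with *or* |
|---|---|---|---|---|
| yes | yes | not excluded | no | not excluded |
| yes | no | not excluded | yes | excluded |
| no | yes | not excluded | yes | excluded |
| no | no | excluded | yes | excluded |

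As written, the criterion catches 1 of the 3 breaching combinations; with *or* it catches all 3. EXCL08 in the SAP is (not A) alone, which agrees with Table 5-2 on the pre-randomization condition and not with Exclusion 8 as worded.

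**The plan's own figure.** Difference 0.15, SD 0.196, two-sided 0.05 and power 0.90 (Protocol Section 9.7) give 36.9 per arm by the two-sample t-test. That rounds to 37, or 74 in total, as stated. Power at 37 per arm is 0.901.

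**Possible size.** The documents give neither the share of recent changers nor the statin effect on TBR. I assume a share p of 5–15% of randomized subjects and a fall r of 0.05–0.15 still to come after the baseline scan. The value 0.15 is an upper bound, because part of a recent change is already present at baseline.

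SD of the change = √(0.196² + p(1−p)r²):

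| p | r | SD | Power, 37 per arm |
|---|---|---|---|
| none | none | 0.1960 | 0.901 |
| 0.05 | 0.05 | 0.1963 | 0.900 |
| 0.10 | 0.10 | 0.1983 | 0.894 |
| 0.15 | 0.15 | 0.2032 | 0.880 |

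For example, 0.10 × 0.90 × 0.10² = 0.0009, and √(0.038416 + 0.0009) = 0.1983.

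**Chance imbalance.** Suppose 8 of the 84 randomized subjects are recent changers, 42 per arm. By the hypergeometric distribution, the chance that the arms differ by 4 or more changers is 0.26, and by 6 or more 0.06. A difference of 4 moves the estimate by r × 4/42, which is 0.0048 at r = 0.05 and 0.0143 at r = 0.15. The standard error is 0.196 × √(2/42) = 0.0428, so the shift is 0.11 to 0.33 of a standard error.

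**The case against.** The strongest reply is that the right rule already exists and binds. Table 5-2 governs these drugs, Exclusion 6 sends every site to that table, and EXCL08 shows that the trial team understood the rule as intended. Harm needs a recent dose change, a literal reading of Exclusion 8 and disregard of Table 5-2, all together. Prior medications over six months are captured at screening, so a recent change would be visible. This stands in part: it makes wrongful entry possible, not certain. It does not remove the conflict, because the eligibility list controls randomization and Exclusion 6 invokes the table only for psoriasis treatments.

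It can also be said that the magnitude is assumed and small. That is correct. At the full 42 per arm, power is 0.934 without contamination and 0.917 in the worst case above, still over 0.90. The losses tabulated apply at 37 per arm, the evaluable number the plan was sized on.

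Code 0 for EXCL08 is no special weakness. Every deviation in SAP Table 5.1 except missing prior consent carries it, in keeping with intention to treat. It means only that the SAP does not undo a wrongful entry.

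Nor are dose changes during the study a separate gap. Deviation COMD01 ("Use of prohibited treatment at any time during the study after randomization") can cover them, and Protocol Section 5.5.7 supplies the data: "Information recorded will include indication for use, dosage, and dates of administration".

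Finally, any protocol change needs a formal amendment under Section 11.1 and cannot affect subjects already randomized. That bears on timing, not on whether the wording is wrong.

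**Conclusion.** The concern holds. Exclusion 8 as worded contradicts Table 5-2 on a factor that the protocol says moves the primary endpoint within its measurement window. This conclusion rests on the wording alone and needs no assumption. The numerical effect does rest on assumptions and is small: a power loss of at most about two percentage points at 37 per arm, and a shift of about a third of a standard error or less if the arms differ by 4 recent changers. There is no systematic bias. The correction should be made because the two rules conflict and the remedy is simple, not because the result is in danger.

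**What to change.** In Exclusion 8, replace *and unable to remain* with **or unable to remain**, and add **(see Table 5-2)**, as Exclusion 6 already does. The criterion then excludes exactly the subjects who breach Table 5-2. No new deviation code is needed. Optionally, add a line to the SAP stating that COMD01 includes post-randomization dose changes of cholesterol-lowering medication.

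The text change is one word and one cross-reference, with no effect on sample size, visits or analysis. It does need a written amendment with the usual approvals, so it can go into the next one. A clarification to sites of how the existing Table 5-2 rule applies would help in the meantime.
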